The PROMIS®, the Patient-Reported Outcomes Measurement Information System, was developed as a set of patient reported outcomes that can assess physical, mental and social health in adults and children.^{76,77} In this study, we propose to use four domains of the PROMIS®-29, which has eight outcome domains important for a study of CLBP in older adults. These include physical function, sleep disturbance, fatigue and ability to participate in social roles. All short-form measures we will use are 4-items except for Physical Function. The RTF recommends the use of pain intensity, pain interference, physical function, depression, anxiety, and sleep disturbance, all domains covered by the PROMIS®-29.⁶⁰ Deyo et al.⁷⁸ found that the PROMIS®-29 measures had good to excellent internal consistency and worse scores among older patients with chronic pain associated with falls, high catastrophizing and worker's compensation, suggesting its value for use with older adults. Hence, we believe the PROMIS measures are best suited for use with our older adult population. However, in the interest of adopting all the required HEAL CDEs, we will add 2-items to the physical function and sleep disturbance questions so that they are the 6-item HEAL core recommended versions of these scales, and substitute the PHQ-4 anxiety depression screener rather than use the PROMIS® anxiety and depression scales. All versions of the multi-item short-forms we are using include the range of mild to severe impairment for that domain and measure at least 3 standard deviations of the T-scores⁸⁰, the healthy population plus roughly two standard deviations of the unhealthy population.⁸¹ Correlations between each multi-item short form we are using and the

full-item bank are above 0.9 for all domains except physical function, where the correlation is roughly 0.87.⁸⁰ Power for detecting a small (0.2) effect in a clinical population for each multi-item measure with our sample sizes is well over 90%.⁸⁰ Construct validity was demonstrated for these measures as well.⁸⁰ Below, we describe other features of the individual PROMIS® short form measures we are using.

Physical Function will be measured by the 6-item PROMIS® physical function measure. It has been found to perform well psychometrically compared to the RMDQ.⁸⁴ It is a secondary outcome.

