9.2 Sample Size and Treatment Assignment Procedures

Older adults with cLBP will be randomized, in equal proportions, to one of three groups: Usual medical care (UMC), standard acupuncture (SA), or enhanced acupuncture (EA).

We determined our sample size requirements for our primary outcome RMDQ at 6-months that focuses on detecting differences of each acupuncture group compared to UMC. Given a sample size of 630 total participants (210 per group) we have at least 90% power to detect a minimally clinically important difference (MCID) of two points on the RMDQ^{29,72} between each acupuncture group and UMC assuming a SD of 6 in each arm (consistent with results from previous

trials)^{25,41,100} and only testing for pairwise comparisons if the omnibus F-test is statistically at a 0.05 α -level (to control for multiple comparisons). Accordingly, we have high power to detect a MCID difference between SA and UMC as well as EA and UMC. Nevertheless, if instead we assume that at 6-months SA attenuates to be equivalent to UMC and EA has a 2-point MCID improvement relative to both SA and UMC we will have 91% power to detect a difference between SA and EA as well as between UMC and EA. Thus, we are sufficiently powered ($\geq 90\%$) to detect MCID differences between all pairwise group comparisons. Power was calculated via simulation studies using R software.

For any two group comparisons, given our sample size of 210 per group and a SD of 6, the minimal detectable difference is 1.15 pts (i.e. the 95% CI width around difference in means between groups is +/- 1.15 pts). Further, for secondary analysis for the binary outcome 30% improvement in RMDQ from baseline we have >90% power to detect an MCID assuming the probability of improvement in UMC was between 33%²⁵ and 44%⁶ and the MCID was a 15% improvement above UMC for each of the acupuncture groups. Assuming a 20% loss-to-follow-up rate we inflated our sample size to 263 per group (789 total) to assure that we are well powered for all analyses of interest. (Assuming a more conservative 25% loss-to-follow-up rate we would inflate our sample size to 280 per group (840 total) to assure that we are well powered for all analyses of interest.) We will use an intent-to-treat approach in which participants will remain as randomized regardless if they withdrawal from treatment or cross-over to other treatment arm (e.g. UMC participant seeks acupuncture outside of study).

Treatment Assignment Procedures

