9.6 Data Analyses

Aim 1 will evaluate the effectiveness of acupuncture and acupuncture plus maintenance relative to Usual Medical Care (UMC) at 3-, 6- (primary time-point), and 12-months after randomization. We will conduct a longitudinal analysis including the continuous outcome, change in Roland Morris Disability Questionnaire (RMDQ) from baseline (primary outcome) measured at all follow-up times, in one model estimated using generalized estimating equations (GEE). We will use a working independence correlation matrix and will calculate standard errors using the robust sandwich estimator to account for within-person and within-provider (some participants may see the same provider) correlation.¹⁰¹ We will include interactions between intervention groups and time (3-, 6-, and 12-months) to estimate time-specific intervention effects. Time will be included as a categorical variable. To gain power, since acupuncture and acupuncture plus maintenance at 3-months are the same intervention (maintenance period occurs between 3 and 6 months post randomization and neither participants in the EA condition nor the acupuncturists treating them will be aware they will receive maintenance treatments until close to the 3-month follow-up), we will combine acupuncture groups at 3-month follow-up. We chose GEE as our analytic method because our primary outcome, RMDQ, is not expected to be normally distributed. From our experience working with RMDQ data, adjusting for baseline RMDQ value results in more normally distributed residuals. However, we didn't want to make that assumption a priori and therefore chose GEE.

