For the 6-month time point we will conduct a sequential series of analyses. We will first run a regression model with three groups (acupuncture [SA], acupuncture plus maintenance [EA] and UMC) for the 6-month follow-up. We will then assess differences in change in RMDQ at 6-months between the two acupuncture groups: with (EA) and without (SA) maintenance. If a statistically significant ($\alpha=0.05$) and meaningful difference (>1 point difference) is found between the maintenance (EA) versus no maintenance (SA) groups (Scenario 1), we will further compare each of the acupuncture groups separately to UMC. Scenario 1 assessments will determine if acupuncture with maintenance (EA) is better than acupuncture without maintenance (SA) at 6-months and if either or both acupuncture groups are better than UMC. If acupuncture groups do not differ at 6-months (Scenario 2), we will combine acupuncture groups for this time point and run a second regression model including only UMC and the combined acupuncture group. If this regression model shows that acupuncture is better than UMC, we will conclude that acupuncture improved RMDQ at 6-months, but maintenance was not shown to be efficacious.

We will follow the same general framework for 12-month as we have specified for 6-months. Note that the analysis focused on the 12-month follow-up timepoint provides an important test of whether maintenance (EA) makes an appreciable difference over standard acupuncture in sustaining or improving the effect of acupuncture on pain-related functioning that endures after the end of treatment. Finally, note that we include all time points in a single model within this general modeling framework to handle correlation due to multiple outcomes on a given person.

To control for multiple comparisons when testing between the three groups at 6-months we will use Fisher's least significant (LSD) difference procedure.¹⁰² Fisher's LSD has been shown to strongly hold the family-wise error rate at α -level for studies with three treatment groups.¹⁰³ Fisher's LSD is a simple procedure where the global Wald-test of the null hypothesis of equal means for all groups is performed first. If this overall test is statistically significant then the sequential series of pairwise comparisons will be performed as outlined previously; otherwise the procedure stops, failing to reject the over null hypothesis that at least one mean is different

from the others.

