We will conduct a similar analysis for secondary and tertiary outcomes, including key secondary outcomes such as the PEG and will use appropriate link functions for non-continuous outcomes. All models will adjust for baseline outcome value, age, sex, and HCS as well as any baseline variables that are predictive of loss to follow-up. All analyses will be conducted following an intent-to-treat approach, including all individuals randomized regardless of their engagement with, or exposure, to the intervention. If loss to follow-up is above 15%, we will employ imputation techniques to address missing data issues.¹⁰⁴ However, our focus will be on minimizing loss to follow-up and in our collective substantial experience conducting similar trials, we have consistently had retention in line with this. The imputation method that we were referencing uses a pattern mixture approach that relaxes the missing at random assumption. This approach that we propose using is derived for GEE and is sensitive to potential non-ignorable missingness.¹⁰⁴

Exploratory analyses will further use tertiary outcome data collected monthly (i.e., the PEG and PROMIS®, Physical Function). We will use these measures to assess the trajectory of how long it takes until patients improve and to address questions such as “What proportion of people improve at three months if they don’t improve after one or two months of acupuncture?” These exploratory analyses will help address how much acupuncture is needed to improve and at what time, given a patient’s outcome trajectory, should acupuncture treatment stop if improvement has not been shown up to that time.

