## **8. Multiple Comparisons**

We have one primary outcome – the change on RMDQ scores for low-back pain related disability at 6 months since baseline. To control for multiple comparisons due to 3 intervention groups we will apply Fisher's Least Significant Difference approach in which first an omnibus Wald-test for any statistically significant difference

between the three groups is evaluated at the 0.05 alpha level. If the omnibus test is statistically significant, then the pair-wise differences are then evaluated, each using two-sided alpha=0.05. If the omnibus test is not statistically significant, we will conclude that there is no benefit of acupuncture for that time point. In addition, secondary analyses will use a similar approach as that described for the primary outcome to control for the three group comparisons.

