## **16. Exploratory Effectiveness Analyses on Tertiary Outcomes at 3-, 6-, and 12-Months**

We will assess the tertiary outcomes including PROMIS measures of ability to engage in social roles, anxiety, depression, fatigue, and sleep disturbance/duration in exploratory analyses. These measures are related to other common complaints which acupuncture treatment may have impact on, so improvements on these metrics after acupuncture treatment will be expected. However, since there are less data linking them to acupuncture, especially in a chronic pain population, we will conduct only exploratory analyses on these outcomes. We will fit models for these outcomes separately similar to the model for secondary outcomes at 3-, 6-, and 12-months as described in Section 15 and observe the estimated effects of acupuncture treatments.

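### The power claimed for a 0.2 effect on each PROMIS scale names no comparison, and the planned between-arm tests do not deliver it unless a high, unstated baseline correlation is assumed

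*Protocol*

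**What the plan says.** The protocol's account of the PROMIS short forms (section 6.2.2, Aim 1 measures) says: "Power for detecting a small (0.2) effect in a clinical population for each multi-item measure with our sample sizes is well over 90" per cent. It cites reference 80, a paper on those instruments. Four scales are concerned: physical function (secondary), and sleep disturbance, fatigue and social roles (tertiary).

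The only worked power calculations in either document are for the RMDQ (Protocol 9.2, SAP 4). They use 210 evaluable per arm, SD 6, a 2-point difference, and pairwise tests made only if a three-group omnibus test passes at 0.05. If only EA works, "we will have 91% power to detect a difference between SA and EA as well as between UMC and EA". Enrolment follows from that: "Assuming a 20% loss-to-follow-up rate we inflated our sample size to 263 per group (789 total").

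The PROMIS analyses follow the RMDQ framework:
- Pooling at 3 months: "we will combine acupuncture groups at 3-month follow-up" (Protocol 9.6).
- Pooling at 6 months, with the same scheme at 12: "If acupuncture groups do not differ at 6-months (Scenario 2), we will combine acupuncture groups for this time point" (Protocol 9.6).
- Adjustment: "All models will adjust for baseline outcome value, age, sex, and HCS" (Protocol 9.6).
- Multiplicity: "secondary analyses will use a similar approach as that described for the primary outcome to control for the three group comparisons" (SAP 8).
- Tertiary scales: "we will conduct only exploratory analyses on these outcomes" (SAP 16).

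**The concern.** The protocol needs 210 evaluable per arm for about 91% power at 0.33 SD. With the same patients and tests, a smaller effect of 0.2 SD cannot have power well above 90% unless something else cuts the variance a good deal, and the sentence names nothing that would. Because it refers to this trial's own sample sizes, a reader can fairly take it as power for the treatment comparison.

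What is at stake is how a null PROMIS result is read, above all for physical function. Someone could cite the sentence as good evidence against a 0.2 SD effect when the test may have had a sizeable chance of missing one.

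**Working it through.** **Inputs.** From the documents: 210 evaluable per arm, 263 randomised per arm and 20% loss (Protocol 9.2, SAP 4); two-sided 0.05 per pair after an omnibus test at 0.05 (SAP 8); 1:1:1 allocation (SAP 7); effect 0.2 (Protocol 6.2.2).

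Assumed: 0.2 is in SDs of the follow-up score, and the baseline-to-follow-up correlation r is 0.5 to 0.7. The documents give no r for any PROMIS scale. For the RMDQ, SAP 4 gives SDs of 5.42 (6 months) and 5.11 (change). If the baseline SD is also 5.42, r = 1 − 5.11²/(2 × 5.42²) = 0.56, inside the assumed range. Clustering by acupuncturist is ignored, which favours the plan.

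**Formula before the omnibus test.** Adjusted effect e = 0.2/√(1 − r²). Power = Φ(e/√(1/n₁ + 1/n₂) − 1.96).

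**Step 1: reproduce the protocol's RMDQ figure.** 2/6 = 0.333 SD. With 210 v 210, √(2/210) = 0.0976, and Φ(0.333/0.0976 − 1.96) = 92.7%. Simulating the procedure (omnibus and pairwise tests both significant, 2,000,000 draws) gives 91.2%, against the stated 91%. The confidence-interval half-width also agrees: 1.96 × 6 × 0.0976 = 1.15.

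**Step 2: the same method at 0.2 SD, unadjusted.**
- Per pair, 210 v 210: Φ(0.2/0.0976 − 1.96) = Φ(0.09) = 53.6%.
- Pooled, 420 v 210: √(1/420 + 1/210) = 0.0845; Φ(0.2/0.0845 − 1.96) = Φ(0.41) = 65.8%.

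**Step 3: add baseline adjustment and the omnibus test.** The gated columns require the omnibus test and the contrast both to be significant, with SA = EA = 0.2 and UMC = 0.

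| Evaluable per arm | r | Pair | Pooled | Pair, gated | Pooled, gated |
|---|---|---|---|---|---|
| 210 | 0 | 54% | 66% | 46% | 53% |
| 210 | 0.5 | 66% | 78% | 59% | 67% |
| 210 | 0.7 | 82% | 91% | 78% | 85% |
| 263 (no dropout) | 0 | 63% | 75% | 56% | 64% |
| 263 (no dropout) | 0.5 | 75% | 86% | 70% | 78% |
| 263 (no dropout) | 0.7 | 89% | 96% | 87% | 92% |

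The ungated pooled column applies at 3 months, where pooling is by design and the test is direct (SAP 13.2). The gated columns apply at 6 and 12 months for the secondary scale. Whether the gate covers the tertiary scales is not stated, so both are shown.

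**Step 4: correlation needed for 90%.** At 210 per arm: 0.77 per pair and 0.68 pooled (gated 0.79 and 0.75). At 263 per arm: 0.71 and 0.58 (gated 0.73 and 0.67).

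**Step 5: effect detectable with 90% power, 210 per arm, ungated.** Per pair, 3.2415 × √(2/210) × √(1 − r²) = 0.32 SD unadjusted, and 0.27 to 0.23 SD at r = 0.5 to 0.7. Pooled, with 1.5/210 in place of 2/210: 0.27 SD, and 0.24 to 0.20 SD.

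**Step 6: a reading that does meet the claim.** For within-person change, with 0.2 in SDs of the change score, power = Φ(0.2√n − 1.96): 98.4% at n = 420 (both acupuncture arms) and 99.9% at n = 630.

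**The case against.** The sentence sits among statements about instrument properties, away from the power section, and cites a paper not available here. It may describe a scale's sensitivity to change within a group, and on that reading the figure is right. SAP 14 speaks of comparing follow-up with baseline, and exploratory within-person trajectories of monthly physical function are planned.

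The correlation range is also assumed. At 210 per arm, pooled ungated power is 94.7% at r = 0.75 and 97.6% at r = 0.80. With 15% loss (224 per arm) it is 92.8% at r = 0.7; with no loss, 96.0%. The unadjusted figures describe an analysis that will not be run, since every model adjusts for baseline.

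Most of this stands as a limit on the conclusion. The figure is not impossible on every reading, its source cannot be checked here, and the adjusted pooled figures are the most relevant. It does not rescue the sentence for the treatment comparisons. SAP 14 goes on to analyse change from baseline in the between-arm RMDQ framework, and per-pair power at r = 0.7 stays below 90% even with no dropout. The pooled cases that pass 90% clearly need a high correlation that neither document states, or set aside the 20% loss the protocol assumes.

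**Conclusion.** The concern holds, and it is minor. At the protocol's own evaluable n and tests, the planned comparisons do not support power well above 90% for a 0.2 SD effect. Within the assumed r of 0.5 to 0.7, the best case is 91%: pooled arms, r = 0.7, no omnibus gate. Per pair the ceiling is 82%, or 78% after the gate.

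This rests on the assumed correlation, on 0.2 being in SDs of the follow-up score, and on ignoring clustering. A sponsor-supplied correlation of 0.75 or more would bring the pooled comparison above 90% before the gate and to about 90% after it.

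The consequence is limited to reading null PROMIS results, mainly for physical function. The sentence supports no sample-size decision, the SAP does not repeat it, and the RMDQ calculation is unaffected.

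**What to change.** Delete the sentence. Alternatively, replace it with power for the planned between-arm comparison, stating whether that is pooled or per pair, the evaluable n, alpha, whether the omnibus test is included, and the baseline correlation with its source.

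Possible wording, with the correlation marked as assumed until the sponsor supplies one: *With 210 evaluable per arm and two-sided alpha 0.05, power for a 0.2 SD effect before the omnibus test is about 66-82% per pair and 78-91% for pooled acupuncture against usual care if the baseline correlation is 0.5-0.7 (assumed), and about 59-78% and 67-85% after it.*

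If the figure is an instrument-level or within-person result from reference 80, say so and do not present it as power for the treatment comparison.

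The cost is one sentence in the protocol, a less favourable stated figure, and the need to name a PROMIS correlation if the claim is kept. Design, sample size and analysis do not change.

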6.2.3 Blinding

This is an unmasked trial for participants, although the acupuncture participants will not know whether they are in the SA group or EA group until 10 weeks into the standard treatment period. Interviewers will be masked to treatment group for all standard study assessments. For qualitative data collection, interviewers are expected to be unmasked to participants treatment condition. Acupuncturists will not know whether their patients are in the SA or EA group until 10 weeks into the standard treatment period.

No members of the Core Executive Team (Multiple PI's, site PI's and the Statistical Methods Committee, which includes the study biostatisticians) will have access to the outcomes data during the trial. Conceivably, a site PI or one of the Multiple PI's may become aware of an individual's treatment group if they have an Adverse Event that requires the investigator intervene. One biostatistician, [name], may be supervising some data collection exercises with the programmers as needed, but datasets will not contain a treatment assignment variable prior to the locking of the database. All other members of the CEC will become unblinded after the data base is locked.

6.2.4 Follow-up Assessments

Each participant will be followed for 12-months post-randomization. Participants will be invited to complete short monthly check-ins per their preferred mode (phone or web) between main assessments at 3-, 6- and 12-months. Monthly check-ins will take less than 5-minutes to complete and will be limited to administration of the PROMIS® Physical Function (6-items) and PEG (3-items). Participants will receive a \$5 incentive for each check-in completed typically payable as a lump sum at the end of the study (up to \$45 total for the 9 monthly check-ins). Patients will be contacted via their preferred mode (phone or web) for the 3-, 6-, and 12-month follow-up surveys. Advance letters will be mailed as reminders to those preferring phone follow-up and emails with the reminder and a live hyperlink will be sent to those preferring to complete follow-ups online. Participants may opt to change their preferred mode at any time. Incentive payments of \$20, \$25 and \$30 will be sent for completing 3-, 6- and 12-month follow-ups, respectively.

6.2.5 Completion/Final Evaluation

The final 12-month assessment will include the same measures as those included in the 3-month follow-up assessment battery.

7. SAFETY ASSESSMENTS

We will monitor patient safety for all individuals during their 12-month enrollment in the trial. Acupuncturists will perform an intake assessment, which will include a thorough understanding of the patient's health relevant to the provision of acupuncture needling. The needling protocol, although broad, is based on care delivered in clinical practice^{47,48,55,99} and the highest quality trials.^{23,25,29,30,45} Our acupuncturists will be trained on the study protocol and reminded of best practices when treating older adults. They will be able to provide enough treatments to allow them to start with gentle treatments at the beginning for patients who are apprehensive about needling.

We will select acupuncturists who have experience working with older adults and cLBP, and, if applicable, are already credentialed to provide acupuncture for patients within the local health care system. We will ensure that they review universal precautions and care guidelines in older adults. We will make sure that the older adults know how to prepare for their treatment (e.g., be fully satiated and hydrated in advance of a needling session). Although treatment is expected to be focused on needling treatment for cLBP, acupuncturists will tailor treatment to the presentation and needs of each participant. Acupuncturists will use only single-use pre-sterilized needles that are immediately discarded after use. This is already required of all acupuncture providers in the US. They will avoid needling areas of the skin that may have rashes or lesions. Finally, patients whose symptoms significantly worsen or who present with any new symptom will be referred to their PCP for evaluation. Medical care of patients invited to participate in the study will not be affected by their decision whether or not to participate.

